3.3 Blinding and Randomization Methods

An open-label study design was chosen since blinding such a study would be problematic due to the different methods of administration and the individualized nature and frequent dose adjustments needed with oral phosphate/active vitamin D therapy. Eligible subjects will be enrolled in the study and sequentially assigned an identification number. Subjects will be randomized 1:1 to receive open-label KRN23 by subcutaneous injection or active control via an Interactive Web Response System (IWRS) based on a randomization schedule developed by an independent third-party vendor. Randomization will be stratified by baseline rickets severity, age, and region.

3.4 Stratification Factors

Stratification factors include baseline rickets severity (RSS total score ≤ 2.5 vs > 2.5) and age (< 5 vs ≥ 5). The randomization was also stratified by region (Japan vs. rest of World) for operational and logistic considerations to ensure balance between the two treatment groups in Japan, as small number of subjects are expected to be enrolled.

3.5 Sample Size Considerations

This Phase 3 study is powered to test the effect of KRN23 on improvement of rickets using RGI-C global score at Week 40 against the active control (oral phosphate and active vitamin D) based on the assumption of a mean RGI-C global score of 1.80 in the KRN23 group, 1.40 in the active control group, and a common standard deviation of 0.50. Given these assumption, a total sample size of 60 (30 per group) will provide approximately 80% power to detect such a difference in the mean RGI-C global score at Week 40 between treatment groups using a two-sample t-test with a two-sided alpha level of 0.05. A 10% drop-out rate is incorporated in the sample size calculation.

The age of eligible subjects will be monitored for enrollment for age distribution. Approximately 20 subjects aged 1 to < 5 years will be included (approximately 10 in each treatment group), and no more than 10 subjects between the ages of 1 to < 3 years will be enrolled. No more than 60% female subjects will be enrolled.

3.6 Primary Analysis

The primary analysis is planned at Week 40.

3.7 Additional Analysis

Additional analysis will be performed at Week 64 to assess the durability of treatment effect, additional efficacy outcomes, and long-term safety. In addition, administrative analyses can be performed to support regulatory activities.

3.8 Data Monitoring Committee

An independent DMC that includes members with expertise in metabolic bone disease, cardiology, and nephrology, and the conduct of clinical trials in children will act in an advisory capacity to monitor subject safety on a routine basis throughout the trial. The DMC will meet at least twice a year during the active-controlled period. The roles and responsibilities of the DMC will be defined in the DMC Charter.

4 STUDY ENDPOINTS AND COVARIATES

All data are collected according to the schedule of assessments ([Appendix 3](#)).

4.1 Primary Efficacy Endpoint

The primary efficacy endpoint is the change in rickets at Week 40 as assessed by the RGI-C global score. The primary endpoint will be compared between the KRN23 and active control (oral phosphate/active vitamin D) groups.

4.2 Secondary Efficacy Endpoint(s)

The secondary endpoints listed in Section [4.2.1](#) and [4.2.2](#) will be compared between the KRN23 and active control groups:

4.2.1 Key Secondary Endpoint(s)

The key secondary endpoints include:

- Change in lower extremity skeletal abnormalities as assessed by the RGI-C long leg score
- Change from baseline in standing height/recumbent length Z score
- Change from baseline in RSS total score
- Change in serum phosphorus from baseline to mean post-baseline values
- Change from baseline in ALP

For the growth-related endpoints RGI-C long leg score and change from baseline in standing height/recumbent length Z score, the primary assessment time will be Week 64. For other key secondary endpoints, the primary assessment time will be Week 40. Because of the small sample size, no multiplicity will be adjusted for the key secondary endpoints.

4.2.2 Other Secondary Endpoint(s)

- Rickets Endpoint(s)
 - Proportion of subjects with a mean RGI-C global score $\geq +2.0$ (substantial healing)
 - Change in rickets as assessed by RGI-C wrist and knee scores
 - Change from baseline in RSS wrist and knee scores
- Growth Endpoint
 - Change in growth velocity Z score from pre-treatment to post-treatment
- PD Endpoint(s)
 - Change from baseline over time in serum phosphorus

- Number of subjects reach the normal range of serum phosphorus (3.2 - 6.1 mg/dL) over time
- Change from baseline over time in serum 1,25(OH)₂D, urinary phosphorus, TmP/GFR and TRP
- Pain, Fatigue and Physical Function Endpoint(s)
 - Change from baseline in the PROMIS (Patient-Reported Outcomes Measurement Information System) scores in Pediatric Pain Interference, Physical Function Mobility and Fatigue domains
 - Change from baseline in the Faces Pain Scale – Revised (FPS-R)
 - Change from baseline in the Six Minute Walk Test (6MWT) total distance and percent of predicted normal

4.3 Safety Endpoints

Safety endpoints will be summarized at Baseline and at each observed time that they are collected. The following endpoints will be examined:

- Frequency (and %), and severity of adverse events (AEs) and serious adverse events (SAEs)
- Prior and concomitant medications
- Change from baseline to post-baseline visits in vital signs and weight
- Physical examinations
- Change from baseline to post-baseline visits in eGFR (calculated using the Bedside Schwartz equation)
- Shift from baseline to post-baseline visits in renal ultrasound in nephrocalcinosis score
- Change from baseline to post-baseline visits in Echocardiogram (ECHO)
- Change from baseline to post-baseline visits in chemistry, hematology, and urinalysis, including additional KRN23/XLH biochemical parameters of interest (serum 25(OH)D; lipase; amylase; creatinine; serum calcium and iPTH, and urinary calcium and creatinine)
- Shift from baseline to post-baseline visits in presence of anti-KRN23 antibody
- Change from baseline to post-baseline visits in Electrocardiogram (ECG)

4.4 Pharmacokinetic Endpoint

- Serum KRN23

4.5 Exploratory Endpoints

- Health-related quality of life: Change from baseline to post-baseline visits in the SF-10 for Children Health Survey (SF-10; for subjects ≥ 5 years of age at the Screening Visit) physical summary score (PHS-10) and psychosocial summary score (PSS-10).
- Dental evaluation: number of dental events in dental caries, tooth extraction, root canal, dental abscesses, and gingivitis assessed at baseline and post-baseline visits.

4.6 Potential Covariate(s)

Unless specified otherwise, the randomization stratification factor (RSS total score ≤ 2.5 vs > 2.5) and age (< 5 vs ≥ 5) will be included as independent variables in the model for efficacy analysis. Region (Japan vs. rest of World) is used for randomization for operational and logistic considerations and will not be used as covariates in any analyses. For the GEE and ANCOVA analyses, baseline result of the response variable will be included as the covariate.

Other potential covariates such as gender might be used in growth analyses. If the baseline RSS total score or age is to be used in the statistical model as a continuous covariate, the corresponding randomization stratification factor will not be included in the same model. Refer to Section 8 for the details of statistical models and covariates for each efficacy endpoint.303, 304

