7.4.3 Method of Assigning Subjects to Treatment Groups

Eligible subjects will be enrolled in the study and sequentially assigned an identification number. Subjects will be randomized 1:1 to receive open-label KRN23 by subcutaneous injection or active control via an Interactive Web Response System (IWRS) based on a randomization schedule developed by an independent third-party vendor. Randomization will be stratified by baseline rickets severity (RSS total score ≤ 2.5 vs > 2.5) and age (< 5 vs ≥ 5 years).

After completion of the 64-week Treatment Period, subjects in Europe, the US, Canada, and Australia who were randomized to KRN23 will continue treatment with KRN23 at their previous dose and regimen in the Treatment Extension Period. Subjects in Europe, the US, Canada, and Australia who were randomized to active control will cross over to receive KRN23 at the starting dose and regimen administered to subjects in the KRN23 arm (starting dose of 0.8 mg/kg Q2W; dose may be increased to 1.2 mg/kg Q2W).

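### Region (Japan vs rest of World) stratifies the randomization but is excluded as a covariate from every model, and the protocol does not list it as a stratum

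*SAP*

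**What the plan says.** SAP 3.3 names three stratification factors: baseline rickets severity, age and region. SAP 3.4 confirms the third: "The randomization was also stratified by region (Japan vs. rest of World"). The reason given is logistic: few subjects were expected in Japan, and the sponsor wanted the arms balanced there.

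SAP 4.6 carries the severity and age factors into the efficacy models by default. Of region it says that it "is used for randomization for operational and logistic considerations and will not be used as covariates in any analyses". Accordingly, the primary ANCOVA in SAP 8.5.3 has treatment, the age stratum and continuous baseline RSS total score. SAP 4.7 still plans summaries by region for baseline characteristics, rickets, growth, PD endpoints, ALP, PK and selected adverse events, descriptively only.

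The current protocol describes a two-factor randomization. Section 7.4.3 states: "Randomization will be stratified by baseline rickets severity", and adds only age. The Synopsis and section 7.1 give the same two factors. The protocol's primary model (Synopsis, Efficacy Analysis; section 7.6.4) adjusts for severity and age. SAP section 3 calls the protocol the definitive reference for the design matters it summarizes, and those include 3.3 and 3.4.

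**The concern.** There are two separate problems.

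First, the documents disagree on how subjects were randomized. The SAP gives three strata and defers to a protocol that gives two. This needs correcting whatever its numerical effect.

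Second, the analysis does not follow the randomization. Balancing the arms on a prognostic factor takes that factor's variance out of the treatment contrast. Leaving the factor out of the model keeps the same variance in the residual. The reported SE, confidence interval and p-value are then wider or larger than the design warrants. An operational reason for stratifying does not alter this. At stake is some power in a trial planned at about 80%. There is no risk of a false positive.

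**Working it through.** **The plan's own figure.** SAP 3.5 assumes "a mean RGI-C global score of 1.80 in the KRN23 group, 1.40 in the active control group, and a common standard deviation of 0.50", tested by a "two-sample t-test with a two-sided alpha level of 0.05". It states that "a total sample size of 60 (30 per group) will provide approximately 80% power" and that "A 10% drop-out rate is incorporated in the sample size calculation". Allocation is 1:1 (SAP 3.3).

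- Normal approximation: n = 2(1.96 + 0.8416)² × 0.50² / 0.40² = 24.5, so 25 per arm.
- Noncentral t: 26 per arm. With dropout, 26/0.90 = 28.9, so 29 per arm or 58 in total. The stated 60 is reproduced to within 2 subjects.
- t-test power is 80.8% at 26 per arm, 82.2% at 27 (30 less 10%) and 86.1% at 30.

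**Inputs the documents do not give.** The Japan count is described only as small; I take 3, 6 and 12 of 60. For the regional gap in RGI-C after adjustment for RSS and age, I take 0.25, 0.5 and 1 residual SD (0.125, 0.25 and 0.5 points at SD 0.50).

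**Analytic effect of omission.** With Japan share p, gap d in residual SDs and exact balance within region, the SE ratio (without/with region) is √(1 + p(1−p)d²). For 6 of 60 and d = 1 this is √(1 + 0.1 × 0.9) = 1.0440.

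Power uses 27 per arm. The true SE is 0.50 × √(2/27) = 0.1361, and 0.40/0.1361 = 2.939. With region (49 df), power is Φ(2.939 − 2.010) = 82.4%. Without region (50 df), it is Φ(2.939 − 2.009 × ratio). Type I error without region is 2[1 − Φ(1.96 × ratio)].

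| Japan of 60 | SE ratio, 0.25 SD | SE ratio, 0.5 SD | SE ratio, 1 SD | Type I error, 1 SD | Power without region, 1 SD |
|---|---|---|---|---|---|
| 3 | 1.0015 | 1.0059 | 1.0235 | 4.5% | 81.2% |
| 6 | 1.0028 | 1.0112 | 1.0440 | 4.1% | 80.0% |
| 12 | 1.0050 | 1.0198 | 1.0770 | 3.5% | 78.1% |

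At 1 SD the power losses against 82.4% are 1.2, 2.4 and 4.3 points. At 0.5 SD with 6 subjects, power is 81.8%, a loss of 0.6 points.

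**Simulation, dropping exact balance.** The planned ANCOVA was fitted with and without region: 6,000 replicates per scenario, assumed permuted blocks of 4 within region × RSS × age strata, 10% dropout. Ratios of mean SE (without/with) were:

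| Japan of 60 | No gap | 0.25 SD | 0.5 SD | 1 SD |
|---|---|---|---|---|
| 3 | 0.992 | 0.994 | 0.998 | 1.017 |
| 6 | 0.995 | 0.998 | 1.006 | 1.039 |
| 12 | 0.997 | 1.002 | 1.017 | 1.076 |

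Simulated power at 1 SD, without versus with region, was 79.6% vs 80.8%, 78.2% vs 80.8%, and 77.5% vs 82.0%. Ratios below 1 show that with very few Japanese subjects and little or no gap, adding region raises the SE, by under 1%.

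Thin strata also matter in another way. With 6 subjects and a 1 SD gap, the mean SE without region (0.1429) was close to the actual spread of the estimates (0.1422). There the loss is mostly real imprecision from imperfect balance. With 12 subjects the SE was clearly too large (0.1476 against 0.1405), and type I error was 3.85%.

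**The case against.** The exclusion is prespecified and explained, and the primary model matches the protocol's. The error is conservative and no bias arises. With a small stratum and a modest gap the effect is close to nil. The 1 SD scenario assumes a regional gap of 0.5 points, larger than the planned treatment effect of 0.40, and nothing in the documents supports it. RGI-C is read centrally by blinded raters, and baseline RSS is already in the model. Moreover, the planning SD of 0.50 belongs to an unadjusted t-test. If it already contains regional variance, power without region stays at the planned level, and adding region is a gain rather than a recovery. Changing the model also means changing the protocol's model text.

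Most of this stands as a limit on size. None of it shows that leaving out a stratification factor is better, or that including it costs more than a degree of freedom and wording.

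Four stronger readings are tempting and are not supported:

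- *That region is shut out of every analysis.* The SAP 4.6 sentence bars it as a covariate, and SAP 4.7 plans descriptive regional summaries.
- *That the SE is too large whenever region is prognostic.* It must be prognostic beyond RSS and age, with near-balanced allocation within region.
- *That the lack of home-health visits makes Japan different.* Protocol 7.1 also exempts Korea, SAP 3.2 adds Italy, and control subjects have no such visits anywhere.
- *That local control-therapy practice makes region prognostic.* No Japanese practice is described. An effect confined to the control arm would be a treatment-by-region interaction, which a region main effect does not capture.

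**Conclusion.** The concern holds in a limited form. The protocol and SAP contradict each other on the strata, and the models omit a factor used to randomize. If region is prognostic given RSS and age and the arms are near-balanced within region, the primary test is conservative.

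The size cannot be fixed at one value, because the Japan count and the regional effect are both assumptions here. The SE excess is about 1% or less with 3 to 6 Japanese subjects and gaps up to 0.5 SD, which is negligible. The 2% to 8% range, with its loss of about 1 to 4 points of power, needs a full 1 SD gap. The case for change rests on consistency between design and analysis at very low cost, not on a demonstrated loss of power.

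**What to change.** - **SAP 4.6 and 8.5.3:** replace the exclusion. Include region (Japan vs rest of World) as a factor in the primary ANCOVA alongside treatment, the age stratum and baseline RSS, and in the ANCOVA and GEE models for the key secondary endpoints. Report the model without region as a sensitivity analysis. Naming both in advance prevents a choice between them after the data are seen.
- **Protocol model text (Synopsis, Efficacy Analysis; 7.6.4):** align it with the revised model.
- **Protocol strata (Synopsis, Study Design and Methodology; 7.1; 7.4.3):** list region as a stratification factor in each place.

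The cost is one degree of freedom (50 to 49 with 54 evaluable subjects), edits to both documents and, if Japan contributes very few subjects and region has little effect, an SE increase of under 1%.

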4.7 Subgroups

Subgroup analysis by baseline rickets severity (RSS total score ≤ 2.5 vs > 2.5), age (< 5 vs ≥ 5) and region (Japan vs the rest of World) will be conducted for the following endpoints:

- Demographics and baseline characteristics
- Efficacy endpoints including rickets, growth, PD endpoints and ALP

The confidence intervals for difference between treatment groups and treatment effect within individual treatment groups will be provided on efficacy endpoints. Subgroup analysis by region will be presented descriptively only.

In addition, subgroup analysis by region will be performed for PK (serum KRN23) and selected AE summaries. Subgroup analysis by gender will be conducted for rickets and growth endpoints. Additional subgroup analysis by PHEX mutation (positive vs non-positive) may be considered if deemed as appropriate. For PROMIS, FPS-R and 6MWT, subgroup analysis by baseline rickets severity (RSS total score ≤ 2.5 vs > 2.5) may be also considered.

5 DEFINITIONS

5.1 Baseline

Baseline is defined as the last assessments prior to or on the date of initiation of the first dose of investigational product.

5.2 Duration of exposure

Duration of exposure in days is defined as: Last date of investigational product – first date of investigational product + 14 days for KRN23 group and Last date of investigational product – first date of investigational product + 1 day for the active control group.

5.3 Study Day

Study day is calculated as:

- (visit date – date of the first dose of investigational product + 1) if the visit date is on or after the first dose of investigational product;
- (visit date – date of the first dose of investigational product) if the visit data is prior the first dose of investigational product.

5.4 Age

Unless specified, the age at baseline in demographics summary will be derived based on the informed consent date:

Age = (Informed Consent Date – Birth Date + 1)/365.25.

Age at study visits for a particular measurement will be derived based on the measurement visit date:

Age = (Visit Date – Birth Date + 1)/365.25.

The age will be rounded down to the nearest x.x years and keep one decimal place.

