5.7 Growth

5.7.1 Standing height/recumbent length Z-score and Percentile

Recumbent length will be measured in subjects < 2 years old or those unable or unwilling to stand for the measurement. Standing height/recumbent length measurements prior to treatment will be abstracted from medical records where available.

Growth as measured by standing height or recumbent length will be evaluated on a percentile basis using the Centers for Disease Control/National Center for Health Statistics (CDC/NCHS) Clinical Growth Charts (Kuczmarski et al. 2000). Data used to produce the United States Growth Charts smoothed percentile curves will be downloaded from the official CDC/NCHS web site: http://www.cdc.gov/growthcharts/percentile_data_files.htm

The data files from the CDC/NCHS that are used for this analysis are summarized below. These files represent the different growth curves for children. LMS refers to the parameters in the CDC Growth Charts Percentile Data Files used to construct the growth curves; these are: the power in the Box-Cox transformation (L); the median (M); and the generalized coefficient of variation (S).

The data files used are:

- Length-for-age charts, birth to 36 months, LMS parameters and selected smoothed recumbent length percentiles in centimeters, by sex and age (LENAGEINF).
- Stature-for-age charts, 2 to 20 years, LMS parameters and selected smoothed stature percentiles in centimeters, by gender and age (STATAGE).

Calculation of Z-scores for length/stature values above and below the median will be performed. Using the CDC/NCHS Clinical Growth Charts, the height-for-age Z score will be calculated using the following equation:

$$Z = \{(X/M)^L - 1\} / (L \times S),$$

where X is the physical measurement (stature in cm) and the LMS parameters are obtained from the appropriate CDC/NCHS Clinical Growth Chart corresponding to the age in months of the child. The percentile corresponding to the Z score is then the corresponding percentile from the standard normal distribution.

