5.7.3 Growth Velocity

Growth velocity of recumbent length/standing height in cm/year will be assessed by a model-based approach. A linear regression model for each subject will be built based on all recumbent length/standing height measurements by assuming a linear change in growth:

$$Y_t = \beta_0 + \beta_1 X_t + \varepsilon_i$$

Where Y_t is the recumbent length/standing height (cm) measured at Time t ; X_t is the time when recumbent length/standing height is measured; β_0 is the intercept, β_1 is the slope of the regression model; ε_i is random error term.

The growth velocity Z score will be calculated based on Tanner's standard (Tanner et al. 1985) in Appendix 6. Let [T1, T2] denotes the age interval (years) where the growth velocity is estimated from, for example, for post-treatment growth velocity at Week 40, T1 = age (years) at baseline and T2 = age (years) at Week 40. The mid-point of the age interval $(T1 + T2)/2$ will be used to locate the closest reference age in the reference table. The corresponding 50th percentile (Mean) and SD values will be used to calculate the growth velocity Z score in the following equation:

$$\text{Growth velocity Z score} = \frac{\text{Growth velocity} - \text{mean}}{\text{SD}}$$

If $(T1 + T2)/2$ is less than 2.25 years, the growth velocity Z score will not be calculated.

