5.8 Percent of Predicted Six-Minute Walk Test

The percent of predicted values will be calculated using published normative data based on age, gender, and height (Geiger et al. 2007). The percent of predicted walking distance 6MWT is given as:

For males:

$$\begin{aligned} & \text{Percent of predicted six minute walk test} \\ &= \frac{\text{Observed 6MWD}}{196.72 + (39.81 * \text{Age}) - (1.36 * \text{Age}^2) + (132.28 * \text{Height})} * 100 \end{aligned}$$

For females:

$$\begin{aligned} & \text{Percent of predicted six minute walk test} \\ &= \frac{\text{Observed 6MWD}}{188.61 + (51.50 * \text{Age}) - (1.86 * \text{Age}^2) + (86.10 * \text{Height})} * 100 \end{aligned}$$

where Age is the subject's age at the time of the assessment (expressed as one digit decimal) calculated using the following: $(\text{date of test} - \text{date of birth})/365.25$, and height is the subject's standing height at the time of the assessment (in m). If there is no height measured at the time of the 6MWT assessment, the closest prior height will be used.

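### Truncated visit ages and nearest-row lookup add avoidable noise to growth-velocity Z, and possibly to height Z because age in months is undefined

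*SAP*

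**What the plan says.** - SAP 5.4: "Age at study visits for a particular measurement will be derived based on the measurement visit date", as days since birth plus one, divided by 365.25. The section ends: "The age will be rounded down to the nearest x.x years and keep one decimal place". No use is exempted.
- SAP 5.7.3: the mid-point of the age interval in years "will be used to locate the closest reference age in the reference table". Appendix 6 is tabulated every half year from 2.5 years. The section gives no interpolation and no rule for a mid-point halfway between two rows. Below a mid-point of 2.25 years no Z is calculated.
- SAP 5.7.1: for height or length Z, "the LMS parameters are obtained from the appropriate CDC/NCHS Clinical Growth Chart corresponding to the age in months of the child". It gives no formula for months and does not refer to 5.4.
- SAP 5.8: percent predicted 6MWT has its own age formula, without the added day, with age "expressed as one digit decimal".
- SAP 4.2.1 lists "Change from baseline in standing height/recumbent length Z score" as a key secondary endpoint; for it "the primary assessment time will be Week 64". Change in growth-velocity Z is among the other secondary endpoints in 4.2.2.

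**The concern.** Age is known to the day for every measurement. Cutting it to a tenth of a year makes a child up to 1.2 months younger on paper, by an amount that differs between visits and depends only on the birth date. Reading a half-year table at its nearest row is coarser still. Two children with the same growth can then receive different Z scores, or one child's Z can jump, for reasons unrelated to growth or treatment. With about 60 subjects, precision on the growth endpoints is scarce and this loss is avoidable. Separately, two analysts who both follow the SAP could compute different height Z values, because age in months is not defined.

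**Working it through.** The documents give no figure for this error, so there is none to reproduce.

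**1. Age error at Week 64.** 64 weeks is 448/365.25 = 1.2266 years. The difference between two truncated ages is 1.2 for 73.4% of children (error -0.0266 y) and 1.3 for 26.6% (error +0.0734 y), depending on the birth date. The mean is -0.0266 × 0.734 + 0.0734 × 0.266 = 0 and the SD is 0.044 y. With the ±3-day visit window the largest error is 0.082 y.

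**2. Row shifts in growth-velocity Z.** Truncation lowers each age by 0.05 y on average, and so the mid-point too. Rows are 0.5 y apart, so about 0.05/0.5 = 10% of children are read from a different row. The exact share depends on the missing tie rule. When the recorded interval is 1.3 y, the truncated mid-point can fall exactly halfway between rows, which happens for 0.0266/0.5 = 5.3% of children. The share is 0.0367/0.5 = 7.3% if ties go up and 7.3% + 5.3%, about 13%, if they go down. Truncation can also push a mid-point below the 2.25-year cut-off.

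**3. Size of the lookup error.** Take a girl growing 6.0 cm/yr with mid-age near 10.75, which is a Week 64 baseline age of 10.75 - 1.2266/2 = 10.14.
- 10.5-year row (6.8, SD 1.1): (6.0 - 6.8)/1.1 = -0.73.
- 11-year row (7.7, SD 1.1): (6.0 - 7.7)/1.1 = -1.55.
- Interpolated at 10.75 (7.25, SD 1.1): (6.0 - 7.25)/1.1 = -1.14.

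She is wrong by about 0.41 Z on either side, and a few days of birth date decide the sign.

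I compared the planned lookup with linear interpolation at the exact mid-age over a range of baseline ages (uniform within age band, Week 64 visit, child at or below the reference mean). The error SD is about 0.03 to 0.08 Z in most bands from 3 to 10, a little higher for girls nearing 10. At baseline ages 10 to 12 it is about 0.18 for boys and 0.30 for girls, with a maximum near 0.9. Nearly all of this comes from the nearest-row rule: with exact ages and the same rule, the SD hardly changes.

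**4. Height Z, only if months come from truncated years.** Error in Z ≈ age error × reference growth rate / height SD. Growth rates are from Appendix 6; the height SDs are assumptions. Largest Week 64 error, using 0.082 y:

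| Age | Growth rate, cm/yr | Assumed height SD, cm | Largest error in change, Z |
|---|---|---|---|
| 2.5 | 8.3 to 8.6 | 3.0 to 4.0 | 0.17 to 0.23 |
| 4 | 7.1 | 4 to 5 | 0.12 to 0.14 |
| 7 | 5.9 | 4.5 to 5.5 | 0.09 to 0.11 |
| 10 | 5.1 | 5.5 to 6.5 | 0.06 to 0.08 |

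Appendix 6 has no rate below 2.5 years; an assumed 10 to 13 cm/yr with SD 2.5 to 3.5 cm gives 0.23 to 0.42 at about age 1. The error SD is about 0.10 Z at 2.5 and 0.05 Z at 7. If the SD of change in Z is 0.25 to 0.6 (assumed), an error SD of 0.05 raises the standard error by 0.3% to 2%, and 0.10 raises it by 1.4% to 8%.

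**5. If months come from exact dates**, the truncation error is zero at every visit.

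**The case against.** The strongest objection concerns height Z. A reader might infer that 5.4 feeds truncated ages into it, so that a key secondary endpoint carries up to 0.2 Z of error. The documents do not support that: 5.7.1 works in months, does not cite 5.4, and nothing says that months are twelve times a truncated year. Nor is 5.4 the only visit-age formula. SAP 5.8 has its own, which suggests that precision may be set endpoint by endpoint. This stands, and the height Z figures are conditional.

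A reader might also infer bias in the treatment comparison. There is no basis for it. Birth dates are unrelated to arm, randomization is stratified by age, and the growth models adjust for continuous baseline age. The error in age change averages zero. Truncation raises Z slightly at each visit, but equally in both arms.

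On velocity Z, the lookup is fully specified apart from ties, and it costs little over much of the range. For boys from 5 to 11.5, adjacent Appendix 6 means differ by at most 0.2 cm/yr, so the error is mostly about 0.1 Z or less. A more dramatic example exists (a boy growing 6.0 cm/yr scores -0.78 or -2.17 either side of mid-age 12.75), but it needs a baseline age of about 12.14, at the edge of an entry range that ends at 12. The girl above is well inside it. For 6MWT the effect is trivial: for an 8-year-old boy 0.1 y changes the predicted distance by 0.1 × (39.81 - 2 × 1.36 × 8) = 1.8 m.

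**Conclusion.** The point holds for growth-velocity Z without any assumption about months: 5.7.3 takes visit ages in years, 5.4 truncates them, and the nearest row is read. The effect is small at most ages and material at baseline ages 10 to 12, where an error SD of 0.2 to 0.3 Z is removable with data already held. These SDs rest on an assumed even spread of ages and on linear interpolation as the standard. The pre-treatment velocity is looked up the same way, so the change in velocity Z carries two such errors. The documents give no SD for that change, so I do not convert this into lost sample size.

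For height Z the finding is that age in months is undefined. Whether there is any error depends on how it is derived, and its size on assumed height SDs. The largest errors would concern the youngest children, and at most 10 subjects are under 3.

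This is a free improvement in precision on secondary endpoints. It does not threaten the RGI-C primary endpoint or the validity of any comparison.

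**What to change.** 1. SAP 5.4 and 5.7.1: state that age in years and in months is calculated unrounded from exact dates for all derivations (months as days/30.4375), and that one-decimal rounding is for display only. For consistency, drop the one-decimal instruction in 5.8; the numerical effect there is negligible.
2. SAP 5.7.3: interpolate the Appendix 6 mean and SD linearly at the exact mid-age. Say what applies between 2.25 and 2.5 years, where the table has no lower row; keeping the 2.5-year row there preserves the present handling. Interpolation also removes the need for a tie rule.

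The second change brings most of the gain for velocity Z; the first settles height Z. The cost is a few sentences in the SAP and a short programming change, with no new data, visits or assessments. Make it before the growth endpoints are analysed.
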